5.3.3 Thrombogenicity Assessment

Arterial and venous thromboembolic AEs, according to ICD-9-CM definitions, will be separately summarized. Temporally-associated events occurring during or within 72 hours post the end of study drug infusion will be separately presented.

5.3.4 Vital Signs

Vital signs will be listed for each subject. Clinically significant vital sign abnormalities will be reported and analyzed as AEs.

5.3.5 Physical Examinations

Physical examination findings (normal and abnormal) will be listed for each subject. Any clinically significant abnormality developed during the clinical study and not already present at screening will be reported and analyzed as an AE.

5.4 Efficacy Analysis

For bleeding episodes, the bleeding duration, severity, achievement of adequate hemostasis, and overall clinical efficacy will be summarized. Also, the number of Fanhdi infusions and the total amount of Fanhdi dosed will be summarized. The proportion of bleeding episodes in which good or excellent clinical efficacy were achieved will also be summarized.

For surgeries or invasive procedures, the surgery type, severity of bleeding episodes, achievement of adequate hemostasis, and overall clinical efficacy will be summarized. Also, the number of Fanhdi infusions and the total amount of Fanhdi dosed will be summarized. The proportion of surgeries or invasive procedures in which good or excellent clinical efficacy were achieved will also be summarized.

For long-term observation, the long-term overall clinical efficacy will be summarized. Also, the number of bleeding episodes and surgeries or invasive procedures will be summarized. The number of infusions, exposure days, and dose per month will be summarized, in addition to the mean quantity of Fanhdi per bleeding episode and/or surgery or invasive procedure.

5.5 Study Size Determination

Approximately 15 subjects are planned to be enrolled in this clinical study. The sample size is based on clinical considerations and was not formally calculated.

5.6 Limitations of Research Methods

The main limitation of the study is the fact that is an observational, non-interventional study. Therefore, confounding factors such as the selection of the population may be present. The inclusion of subjects will be done arbitrarily by the investigators in the context of clinical practice. The source of data will be available in the investigator's department and the sponsor or its representatives will have access thereto. However, some details in the subjects' medical records may not have been previously collected in the medical history of the subjects. The sponsor will have a special interest in resolving this possible problem of classification (eg, the absence of diagnostic records or a lack of information regarding tolerance of the treatment) and will attempt to verify the data sources insofar as it is possible. Efforts to reduce potential errors will be discussed with the investigators to the extent possible.

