3 STUDY DESIGN

3.1 Study Design and Plan

This is a Phase 4, observational, multi-center, prospective, post-authorization cohort study examining the safety (immunogenicity and thrombogenicity) and overall clinical efficacy of long term use of Fanhdi in routine clinical practice in approximately 15 subjects with VWD. In this clinical study, subjects will be treated with Fanhdi according to the investigator's standard of care to achieve hemostasis. Enrolled subjects will be treated with Fanhdi as their sole source of VWF/FVIII concentrate for prophylaxis and treatment of all bleeding episodes and surgical or invasive procedures for an observational period of 12 months.

Data will be collected from the information generated during routine examinations and treatments as performed by the investigator per standard of care during an observation period of 12 months, starting with the first Fanhdi infusion. There will be no intervention with the prescribing habits or practices of the investigator's standard of care, however the investigator is expected to treat the subject within the approved labeling for dose and frequency of Fanhdi as described in [Section 3.1.1 \(23\)](#). Data collection for all subjects will include inhibitor development (immunogenicity), thrombogenicity, adverse events (AEs), bleeding episodes (spontaneous or traumatic bleeding), surgery or invasive procedure, duration and severity, assessment and achievement of hemostasis, and Fanhdi consumption. Data will be transcribed into electronic case report forms (eCRFs) by designated study center personnel.

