3.2.2 Exclusion Criteria

Subjects with data meeting any of the following exclusion criteria are NOT eligible for participation in this study:

1. Subjects diagnosed with acquired VWD.
2. Subjects with a congenital or acquired platelet function disorder or other concomitant processes that may interfere with coagulation.
3. Subjects who are positive for anti-VWF or anti-FVIII antibodies (≥ 0.5 Bethesda units [BU]) or has been positive in the history of their disease.
4. Subjects with a known intolerance to any substance contained in Fanhdi.
5. Subjects with a history of anaphylactic reactions to blood or blood components.
6. Subjects who are participating in another clinical study involving an investigational treatment or have participated in one in the past 4 weeks.
7. Subjects who, in the opinion of the investigator, may have compliance problems with the protocol.

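### Section 5.6 has investigators include subjects arbitrarily and takes no step to limit or record selection in an uncontrolled cohort of about 15

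*Protocol*

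**What the plan says.** Section 5.6 of the protocol (Limitations of Research Methods) gives the observational, non-interventional character of the study as its main limitation and continues: "Therefore, confounding factors such as the selection of the population may be present". The next sentence describes how subjects enter: "The inclusion of subjects will be done arbitrarily by the investigators in the context of clinical practice". The rest of the section deals with incomplete medical records and verification of sources, and ends: "Efforts to reduce potential errors will be discussed with the investigators to the extent possible".

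The surrounding design is as follows.

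- Section 3.1: "This is a Phase 4, observational, multi-center, prospective, post-authorization cohort study". Everyone receives the product: "Enrolled subjects will be treated with Fanhdi as their sole source of VWF/FVIII concentrate". No comparator is described.
- Section 5.5: about 15 subjects. "The sample size is based on clinical considerations and was not formally calculated".
- Section 5.1: all enrolled subjects form the only analysis population, for both safety and efficacy.
- Sections 3.2.1 and 3.2.2 set eligibility. Some criteria call for judgement, such as inclusion criterion 3 (bleeding or surgery expected in future) and exclusion criterion 7: "Subjects who, in the opinion of the investigator, may have compliance problems with the protocol".
- Sections 3.4, 3.5.2.1, 3.5.2.2 and 3.5.2.3: the investigator rates hemostasis and overall efficacy on the 4-point scale.

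**The concern.** With no control group, every result describes the people who happened to be enrolled. The protocol lets the treating investigator choose them with no stated order or rule, and the same investigator later rates the response. Inclusion criterion 2 requires previous treatment with VWF concentrates and does not rule out previous Fanhdi, so the investigator may already know how a candidate responds.

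The results at stake are the proportions of bleeding episodes and of procedures rated good or excellent (Section 5.4), the prevalence of suspected adverse drug reactions (Section 5.3.1), and the inhibitor and thromboembolic findings (Sections 5.3.2 and 5.3.3). Section 1.2 says a regulator requested the study and that it collects data on use in routine practice, so how far the enrolled subjects represent treated patients is central to its purpose. Without a count of eligible patients who were not enrolled, a reader cannot judge this.

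**Working it through.** The protocol gives no rate, effect size or formal sample-size calculation, so there is no planned figure to reproduce. The check is first a reading of the text, then an illustration of scale.

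**1. Does any section limit or record selection?**

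- Sections 3.2.1 and 3.2.2 define who may be enrolled. They do not say which eligible patients are to be approached.
- Section 3.5 says that the records of all subjects who meet eligibility are reviewed. This concerns data collection and does not require all of them to be invited.
- Section 5.6 names selection as a possible confounder, but its remedies concern missing details and errors in the data.
- Section 5 leaves data handling and evaluation to the statistical analysis plan. The enrolment method is neither.

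So the only statement on how eligible patients are chosen is the sentence in Section 5.6.

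**2. Does the observational design force this?** Section 5.6 presents selection as following from the design. But Section 3.1 bars interference with prescribing; it says nothing against an order of invitation. Inviting eligible patients in sequence changes no treatment, test or visit. Selection by the investigator among eligible patients can therefore be reduced.

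**3. Illustration of scale (assumptions, not protocol figures).** Let p be the true subject-level proportion with a given outcome among eligible patients, and r the chance that such a patient is included relative to the others. The expected proportion among those enrolled is

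q = p·r / (p·r + 1 − p).

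*Success, p = 0.80:*

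| r | Calculation | q |
|---|---|---|
| 0.5 | 0.40 / (0.40 + 0.20) | 66.7% |
| 1 | 0.80 / (0.80 + 0.20) | 80.0% |
| 1.5 | 1.20 / (1.20 + 0.20) | 85.7% |
| 2 | 1.60 / (1.60 + 0.20) | 88.9% |
| 3 | 2.40 / (2.40 + 0.20) | 92.3% |

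*Safety event, p = 0.05, 15 subjects, chance of seeing at least one event = 1 − (1 − q)^15:*

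| r | q | Chance of at least one event |
|---|---|---|
| 0.25 | 0.0125 / 0.9625 = 0.0130 | 17.8% |
| 0.5 | 0.025 / 0.975 = 0.0256 | 32.3% |
| 1 | 0.0500 | 53.7% |
| 2 | 0.10 / 1.05 = 0.0952 | 77.7% |

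The result moves either way according to r, and the protocol offers nothing from which r could be estimated. A confidence interval does not help: no events in 15 subjects gives an exact one-sided 95% upper limit of 1 − 0.05^(1/15) = 18.1%, but only for the kind of patient actually sampled.

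These are subject-level figures. The good/excellent proportions in Section 5.4 are per bleeding episode and per procedure. One subject may contribute several or none, so the figures do not carry over directly.

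**The case against.** The strongest defence is that Section 5.6 is disclosure. The word *arbitrarily* may be loose wording for clinical discretion, the eligibility criteria bound that discretion, and all analyses are descriptive, so no test or error rate is affected. This is fair as far as it goes. But discretion with no order of invitation and no count leaves the same gap, and naming a limitation does not reduce or measure it.

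Some stronger readings are tempting but not supported:

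- *Efficacy is biased upward and reactions downward.* The protocol does not show this. Inclusion criterion 3 draws in patients who are bleeding or expected to bleed or need surgery, so discretion could equally favour difficult cases. Criterion 2 requires earlier VWF concentrate, not earlier Fanhdi.
- *Three of 15 places filled differently shift success by 20 percentage points.* The number of swaps is invented, each swap is assumed to turn a certain failure into a certain success, and the unit is wrong for proportions counted per episode or per procedure.
- *The protocol calls selection its main limitation.* It gives that place to the observational design; selection is an example of what may follow.
- *The investigator alone judges causality.* Under Section 4.4 the sponsor also makes its own assessment. The point about the same person choosing and rating applies to efficacy.

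It is also true that consecutive invitation would not remove all selection. Eligibility begins with patients who will be treated with Fanhdi, so patients not prescribed it never appear. Exclusion criteria 3 to 5 remove patients with past inhibitors, known intolerance or earlier anaphylaxis by design. Finally, a detailed log of patients who have not consented could conflict with Sections 6.2 and 6.3 in so small a population, so any log must be minimal.

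**Conclusion.** The point holds in a limited form. The protocol states a poor rule for choosing among eligible patients, concedes the consequence, and does nothing to limit or measure it. In a single-arm cohort of about 15 whose investigators also rate efficacy, this weakens what the efficacy proportions and safety frequencies can be said to represent. The direction and size of any bias cannot be determined from the document; the percentages in the working show only how an assumed imbalance in inclusion would act. The finding rests on the text of Section 5.6 and on the absence of any invitation rule or count elsewhere in the protocol. It does not depend on what a statistical analysis plan may contain. This is a cheap improvement and does not invalidate the study.

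**What to change.** Replace the sentence on arbitrary inclusion in Section 5.6, and add the rule to Section 3.2, with wording such as:

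*Each center will invite consecutively all patients who meet the eligibility criteria and will be treated with Fanhdi. Each center will keep a log, without identifying data, of the numbers eligible, invited and enrolled and the reasons for non-inclusion, subject to local data-protection rules. These counts, and enrolled subjects' prior use of Fanhdi, will be reported.*

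Exclusion criterion 7 can stay; the log would show how often a judgement that a patient "may have compliance problems with the protocol" was the reason for non-inclusion. If enrolment has begun, the counts that can still be recovered and prior Fanhdi use remain worth reporting.

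The cost is minor paperwork at each center, with no added patients, tests or staff and no effect on prescribing. Selection through prescribing, consent, choice of center and the exclusion criteria remains, and Section 5.6 should continue to disclose it.

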5.7 Premature Termination of Study/Closure of Center

The sponsor, EC, and/or regulatory authorities have the right to close this study or a study center, and the investigator/sponsor has the right to close a center, at any time, although this should occur only after consultation between involved parties. The EC must be informed. Should the study center be closed prematurely, all study materials (except documentation that has to remain stored at the study center) must be returned to the sponsor. The investigator will retain all other documents until notification given by the sponsor for destruction.

A study center can be closed for the following reasons:

- Lack of enrollment
- Non-compliance with the requirements of the study protocol
- Non-compliance with ICH GCP

6 PROTECTION OF HUMAN SUBJECTS

The procedures set out in this protocol pertaining to the conduct, evaluation, and documentation of this study is designed to ensure that the sponsor and investigator continue to abide by the ICH GCP guidelines. The study must also be carried out in keeping with applicable local laws and regulations.

Modifications to the study protocol may not be implemented by the sponsor or the investigator without agreement between both parties.

6.1 Ethics Committee

Documented approval from appropriate ECs must be obtained for all participating study centers prior to study start. Upon request, ECs must provide the sponsor with a list of all members involved in the voting and a statement in which it is declared that the EC is organized and operates according to GCP and applicable laws. When necessary, an extension, modification, or renewal of the approval of the EC shall be obtained and sent to the sponsor.

6.2 Subject Information and Informed Consent

Subject information and ICF will be provided to investigator study centers. Prior to the beginning of the study, the investigator must have the EC written approval/favorable opinion of the written ICF and any other written information to be provided to subjects. The written approval of the EC together with the approved subject information/ICF must be filed in the study files and a copy of the documents must also be provided to the sponsor by the investigator study center.

Written informed consent must be obtained before any study specific procedure takes place. Participation in the study and date of informed consent given by the subject should be documented appropriately in the subject's files. A signed copy of the subject ICF will be provided to the subject or subject's authorized representative.

6.3 Confidentiality

All records identifying the subjects must be kept confidential and, to the extent permitted by applicable laws and/or regulations, they may not be made publicly available.

Subject names may not be provided to the sponsor. Only the subject number is to be recorded in the eCRF, and if a subject's name should appear on any document, it must be deleted before a copy of the document may be supplied to the sponsor. Study findings stored on a computer must be stored in accordance with local data protection laws. Subjects must be informed in writing that representatives of the sponsor, the EC, or the regulatory authorities may inspect their medical records to verify the information collected, and that all personal information made available for an audit or inspection will be handled in strictest confidence and in accordance with local laws if they allow for the patients' information to be identified.

7 STUDY PERSONNEL

Information regarding key personnel involved in the conduct of the study, including the names and contact details of participating study centers, monitors, clinical laboratories, technical departments, and/or institutions, as well as information on members of additional committees, will be kept in the study file of the sponsor and at the participating study centers together with the study reference manual/file.

8 USE OF DATA AND COMMUNICATION OF STUDY RESULTS

Institution and the investigator agree that the first publication shall be made in conjunction with the presentation of a joint, multi-center publication of the study results from all appropriate study centers. If such a multi-center publication is not submitted within 12 months after conclusion of the study at all study centers or after Grifols confirms there will be no joint, multi-center publication, then institution and/or investigator shall have the right, at their discretion, to publish, either in writing or orally, the results of the study performed under the protocol, subject to the conditions outlined below:

- The results of the study will be reported in the publicly accessible registry(ies).
- Institution and/or investigator shall furnish Grifols with a copy of any proposed publication at least 30 days in advance of the date of submission for publication.
- Within said 30 day period, Grifols shall:
 - Review such proposed publication for Confidential Information (other than Study results) and for subject information subject to applicable privacy laws;
 - Review such proposed publication for the unauthorized use of the name, symbols and/or trademarks of Grifols;
 - By written notice to the investigator, identify with specificity the text or graphics in such proposed publication that Grifols contends contains Confidential Information, protected subject information, or the unauthorized use of Grifols' name, symbols and/or trademarks so that the proposed publication may be edited appropriately to remove such text or graphics before publication; and
 - By written request, Grifols may delay proposed publications up to 60 days to allow Grifols to protect its interests in Grifols Inventions described in such publications.

Institution and/or investigator shall give Grifols the option of receiving an acknowledgment for its sponsorship of the study in all such publications or presentation.

Appendix 1 **Summary of Changes for Amendment 2**

(Note: Administrative changes including minor administrative corrections and the changes in the protocol synopsis are not included in Protocol Summary of Changes.)

Sections	Change From: (Version 2.0, dated 07 Feb 2018)	Change To: (Version 3.0, dated 14 May 2018)	Rationale:
Synopsis, Section 3.2.1	
Inclusion Criteria:
 
A subject who will be treated with Fanhdi must meet all the following inclusion criteria to be eligible for participation in this study:
 
 1. Male or female subjects ≥ 18 years of age diagnosed with hereditary VWD of any type and severity who require replacement therapy with VWF/FVIII concentrates. 	
Inclusion Criteria:
 
A subject who will be treated with Fanhdi must meet all the following inclusion criteria to be eligible for participation in this study:
 
 1. Male or female subjects ≥ 18 years of age diagnosed with hereditary VWD of any type and severity who require replacement therapy with VWF/FVIII concentrates when desmopressin (DDAVP) treatment alone is ineffective or contra-indicated. 	Per the Ethics Committee request to provide the clarification on the Fanhdi indication.
